4.1 Rationale for study design

The clinical development program of fingolimod has demonstrated the efficacy and safety of fingolimod 0.5 mg/day dose for the treatment of participants with relapsing-remitting multiple sclerosis globally in clinical studies (CFTY720D2301, CFTY720D2309). Nonetheless there was no data from Chinese participants. Along with the local approval of fingolimod to treat RMS in China on 12-Jul-2019, National Medical Products Administration (NMPA) in China requested, as a post-approval requirement, to collect the efficacy and safety data of fingolimod 0.5mg/day in Chinese participants, including number of pediatric participants recruited will be based on natural occurrence.

This study is designed with the aim to obtain the efficacy, safety and health outcome data in Chinese RMS participants treated with fingolimod for 24 months. Given the limited population size of RMS patients in China because of the rare disease feature, and the concern that a placebo controlled arm is deemed as unethical to participant because of other available DMTs in China, an open-label, single arm design is considered to be adequate for this study, as fingolimod is an approved therapy and continues to be effective and safe for RMS participants across various countries in the world.

4.2 Rationale for dose/regimen and duration of treatment

The dose of Gilenya for participants enrolled in this study is set at 0.5 mg orally administered once daily. The dosage of 0.5 mg has been approved in China for the treatment of relapsing multiple sclerosis in adults and pediatric participants with age ≥ 10 years old and weight > 40 kg.

4.3 Rationale for choice of control drugs (comparator/placebo) or combination drugs

Not applicable

4.5 Risks and benefits

The risk to participants in this study will be minimized by compliance with inclusion/exclusion criteria, close clinical monitoring, avoidance of prohibited treatments and adherence to investigator guidance regarding specific safety areas.

The risk profile of fingolimod includes bradyarrhythmia (including conduction effects) occurring post first dose, liver transaminase elevation, infection, macular edema, hypertension, clinically relevant bronchoconstriction and posterior reversible encephalopathy syndrome.

Women of child bearing potential must be informed that taking the study treatment may involve unknown risks to the fetus if pregnancy were to occur during the study, and agree that in order to participate in the study they must adhere to the contraception requirements outlined in the protocol. If there is any question that the participant will not reliably comply, they should not be entered or continue in the study.

There is currently no data to inform incidence or severity of COVID-19 in patients receiving fingolimod. The immune system effects of fingolimod, integral to their mechanism of action in multiple sclerosis, may increase the risk of infections (including viral infections), as disclosed in the product label of drug.

Patients receiving fingolimod, who may have been exposed to individuals with COVID-19, who are experiencing protracted flu-like symptoms (particularly shortness of breath) consistent with COVID-19, or are confirmed to have COVID-19, should inform treatment physician as soon as possible. Whether there will be interruption of the use of fingolimod will be based on investigator's judgement.

4.5.1 Imaging Risk

A gadolinium-based contrast agent (GBCA) will be administered as an i.v. bolus during each MRI session. There is recent evidence of gadolinium deposition in brain tissues following use of GBCAs. Although no symptoms or diseases linked to gadolinium accumulation in the brain have been identified, health authorities took a precautionary approach (e.g., GBCA EMA restriction re brain deposit), noting that data on the long-term effects in the brain are limited. This led to the suspension of several linear GBCAs and the recommendation that another class of GBCAs known as macrocyclic agents be used as an alternative solution, as they are deemed more stable and have a lower propensity to release gadolinium than linear agents. Although this is highly debated, the current belief is that such agents, especially the linear gadolinium agents, may also increase the risk of a rare but serious disease called nephrogenic systemic fibrosis

(NFS). Few studies showed that use of linear agents in patients with normal kidney function or mild-to-moderate CKD (stage 3; eGFR 30-59 ml/min per 1.73 m²) is without clinically significant risk of nephrogenic systemic fibrosis (NFS) ([Ledneva et al 2009](#)), however they should remain contraindicated in patients with acute kidney injury (AKI) or severe renal disease (stage 4 or 5 chronic kidney disease, CKD) (eGFR <30 ml/ min per 1.73 m²). To prevent this risk and in accordance with health authority guidance (e.g., GBCA FDA guidance re NFS, GBCA UK HA (Health Authority) guidance re NFS), people with severe kidney failure, patients with previous severe allergic/anaphylactoid reaction to a gadolinium-based contrast agent; patients with severe renal disease (eGFR <30 mL/min/1.73 m²), or acutely deteriorating renal function, who would be at risk of nephrogenic systemic fibrosis should be excluded from participating in this study as stipulated in the exclusion criterion.

4.6 Rationale for Public Health Emergency mitigation procedures

During a Public Health emergency as declared by Local or Regional authorities i.e. pandemic, epidemic or natural disaster, mitigation procedures to ensure participant safety and trial integrity may be implemented. Notification of the Public health emergency as declared by local or regional authorities should be discussed among investigators and Novartis. All procedures adapted to the situation must be submitted, if required as per local regulations, through a protocol amendment for approval by local or regional Health Authorities and Ethics Committees prior to implementation of mitigation procedures. The measures (refer to Section 4.6 Rationale for Public Health Emergency mitigation procedures; Section 6.7 Preparation and dispensation; Section 7 Informed consent procedures and Section 8 Visit schedule and assessments for details) provide the possibility to collect safety information remotely, ship IMP directly to patients' home, collect PRO remotely and conduct consent remotely in situation it is not safe for the participants to attend on-site visit. The measures are temporary and should only be used in justified cases as assessed by the investigator.

5 Population

The study population will consist of adult relapsing multiple sclerosis participants aged 18-65 years (inclusive) and in pediatric relapsing multiple sclerosis participants of 10 years of age and older weighing more than 40kg.

Approximately 100 patients will be enrolled from around 10 to 15 centers in China.

5.1 Inclusion criteria

Participants eligible for inclusion in this study must meet **all** of the following criteria at screening:

1. Written informed consent must be obtained before any assessment is performed.
2. Male or Female with age:
18 to 65 years old inclusive;
10 to 17 years old inclusive with weight > 40kg.
3. Clinical definite diagnosis of Multiple Sclerosis according to the 2010 Revised McDonald criteria [Polman et al 2011](#) (refer to [Section 16.3](#)).

4. Participants with a diagnosis of relapsing multiple sclerosis prior to their enrollment to the study (signing the study consent form):
 - At least two documented relapses during the past 2 years, or
 - At least one documented relapse during the last year
5. With RMS that never used fingolimod before enrollment (including naive participants and participants who switched from previous DMTs).
6. Participants with EDSS score of 0 - 6.0 (inclusive) at Screening.

5.2 Exclusion criteria

Participants meeting any of the following criteria at screening will not be eligible for this study.

1. History of myocardial infarction, unstable angina pectoris, stroke/transient ischemic attack, decompensated heart failure with hospitalization or New York Heart Association (NYHA) Class III/IV heart failure (refer to [Section 16.2](#) in the previous 6 months).
2. Treatment with Class Ia or Class III anti-arrhythmic drugs.
3. History or presence of Mobitz Type II 2nd degree or 3rd degree AV block or sick sinus syndrome, unless the participant has a pacemaker.
4. Screening and Baseline QTc interval \geq 500 msec.
5. History of symptomatic bradycardia or recurrent syncope.
6. History of cardiac arrest, uncontrolled hypertension or severe sleep apnea.
7. Macular edema during screening visit.
8. Increased risk for opportunistic infections, including immunocompromised participants :
 - currently receiving immunosuppressive therapies
 - immunocompromised by prior therapies where in the respective approved medication labels suggested wash out of the previous ongoing MS Disease Modifying Therapies (DMT) is not being conducted prior to ICF
 - absolute lymphocyte count is below $0.2 \times 10^9/L$
9. Known active malignancies.
10. Use of teriflunomide within 3.5 months prior to baseline, except if active washout (with either cholestyramine or activated charcoal) was done prior to fingolimod first dose in study.
11. Under MS investigational drug clinical study.
12. Severe active infections, active chronic infections (hepatitis, tuberculosis), as assessed by the treating physician.
13. Severe liver impairment (Child-Pugh class C).
14. Pregnant or nursing woman or woman of child-bearing potential not using highly effective contraception.

Women of child-bearing potential, defined as all women physiologically capable of becoming pregnant. Highly effective contraception methods include:

- Total abstinence (when this is in line with the preferred and usual lifestyle of the

participant. Periodic abstinence (e.g. calendar, ovulation, symptothermal, post-ovulation methods) and withdrawal are not acceptable methods of contraception.

- Female sterilization (have had surgical bilateral oophorectomy with or without hysterectomy), total hysterectomy, or bilateral tubal ligation at least six weeks before taking study treatment. In case of oophorectomy alone, only when the reproductive status of the woman has been confirmed by follow up hormone level assessment.
- Use of oral, (estrogen and progesterone), injected, or implanted hormonal methods of contraception or placement of an intrauterine device (IUD) or intrauterine system (IUS), or other forms of hormonal contraception that have comparable efficacy (failure rate < 1%), for example hormone vaginal ring or transdermal hormone contraception.

In case of use of oral contraception women should have been stable on the same pill for a minimum of 3 months before taking study treatment.

Women are considered post-menopausal if they have had 12 months of natural (spontaneous) amenorrhea with an appropriate clinical profile (e.g. age appropriate history of vasomotor symptoms)). Women are considered not of child bearing potential if they are post-menopausal or have had surgical bilateral oophorectomy (with or without hysterectomy), total hysterectomy or bilateral tubal ligation at least six weeks ago. In the case of oophorectomy alone, only when the reproductive status of the woman has been confirmed by follow up hormone level assessment is she considered not of child bearing potential.

15. Pediatric participant without confirmed history of chickenpox or confirmed documentation of a full vaccination course against varicella zoster virus.
16. Any disability that may prevent the participants from completing all study requirements, as assessed by the treating physician (e.g., mental disorder, blindness or deafness that is not appropriate for age, severe language difficulty).
17. Current medical or neurological condition that might impact efficacy assessments e.g. dementia, schizophrenia, bipolar disorder, major depression, history of multiple traumatic brain injuries, alcohol/drug abuse or dependence currently, or dependence within the last two years.
18. Advanced, severe progressive or unstable disease that may interfere with the safety, tolerability and study assessments, or put the participant at special risk, e.g. uncontrolled diabetes ((hemoglobin A1c (HbA1c)>9%)), severe uncontrolled respiratory disease (including but not limited to pulmonary fibrosis, abnormal pulmonary function tests values lower than 70% of predicted at screening), human immunodeficiency virus (HIV) infection, severe renal impairment.
19. Patient intolerant to undergo MRI or presents contraindications to MRI (e.g., metallic implants, metallic foreign bodies, pacemaker, defibrillator) and the use of gadolinium-based agents (e.g. people with severe kidney failure, patients with previous severe allergic/anaphylactoid reaction to a gadolinium-based contrast agent; patients with

severe renal disease (eGFR<30 mL/min/1.73 m²), or acutely deteriorating renal function, who would be at risk of nephrogenic systemic fibrosis).

20. History of hypersensitivity to any of the Gilenya ingredients.
21. Participant will be excluded from participation, if they have participated in any other unapproved therapy clinical study within last 6 months of the ICF signature date.

6 Treatment

6.1 Study treatment

It is a single-arm, open-label study. The participants will take capsules of 0.5 mg fingolimod for oral administration.

6.1.1 Investigational and control drugs

Table 6-1 Investigational drug

Investigational Drug (Name and Strength)	Pharmaceutical Dosage Form	Route of Administration	Supply Type	Sponsor (global or local)
Fingolimod (Gilenya) 0.5mg	Capsule	Oral use	Open label	Sponsor (global)

6.1.2 Additional study treatments

No other treatment beyond investigational drug is included in this trial.

6.1.3 Treatment arms/group

All participants will receive open-label fingolimod 0.5 mg, orally, once daily.

6.1.4 Treatment duration

The planned duration of treatment is 24 months. Participants may be discontinued from treatment earlier due to unacceptable toxicity whether it is related to study drug or not, disease progression and/or treatment is discontinued at the discretion of the investigator or the decision of participant or serious non-compliance to study protocol. For participants who in the opinion of the investigator are still deriving clinical benefit from fingolimod, every effort will be made to continue provision of study treatment.

6.2 Other treatment(s)

6.2.1 Concomitant therapy

All drug used in previous MS disease modifying treatment should be captured on the "Previous MS disease modifying Treatment" eCRF.

All other concomitant medications taken within 30 days prior to Screening and during the study the respective information needs to be recorded in the eCRF. The investigator should instruct

the participant to notify the study site about any new medications he/she takes after the start of the study drug. Both the start date and the end date, for each medication should be captured on the Concomitant Medication CRF.

Use of the following treatments are recommended to manage potential adverse reactions associated with the study drug:

- anticholinergics (atropine s.c. or i.v.) for treatment of symptomatic bradycardia as the first line treatment, up to 3 mg/day;
- beta-agonists/sympathomimetics (dopamine drip 5-20 µg/kg/min or epinephrine drip 2-10 µg/min) for treatment of non-responsive bradycardia.

For more recommendations for management of bradycardia, refer to [Section 16.5](#).

A short course of intravascular corticosteroids (methylprednisolone) is allowed for the treatment of MS relapses.

The medications allowed for treatment of adverse reactions and MS relapses are not considered study supplies, and therefore, need to be supplied by the study site or only 0.5mg fingolimod will be supplied by sponsor.

6.2.2 Prohibited medication

Use of the following treatments are NOT allowed during the whole course of the study (use can be considered if the study drug has been permanently discontinued):

- anti-neoplastic;
- immunomodulatory or immunosuppressive therapies should be prohibited due to the risk of additive immune system effects (e.g. cyclosporine, azathioprine, methotrexate, cyclophosphamide);
- other concomitant treatment: immunoglobulins (IGs), monoclonal antibodies (including rituximab), other MS DMTs (including but not limited to IFN- β , teriflunomide), adrenocorticotropic hormone (ACTH);
- during and for up to two months after treatment with fingolimod, vaccination may be less effective. The use of live attenuated vaccines may carry a risk of infections and should therefore be avoided.

6.2.3 Rescue medication

Not applicable.

6.3 Participant numbering, treatment assignment, randomization

6.3.1 Participant numbering

Each participant is identified in the study by a Participant Number (Participant No.), that is assigned when the participant is first enrolled for screening and is retained as the primary identifier for the participant throughout his/her entire participation in the study. The Participant No. consists of the Center Number (Center No.) (as assigned by Novartis to the investigative site) with a sequential participant number suffixed to it (assigned by the investigator), so that

each participant is numbered uniquely across the entire database. Upon signing the informed consent form (ICF), the participant is assigned to the next sequential Participant No. available.

6.3.2 Treatment assignment, randomization

No randomization will be performed in this study. There is only one treatment arm in this study, which is fingolimod 0.5 mg, orally, once daily.

6.4 Treatment blinding

As this study is open-label single arm study, treatment will not be blinded during the course of the study.

6.5 Dose escalation and dose modification

6.5.1 Dose modifications

Not applicable.

6.5.2 Follow-up for toxicities

6.5.2.1 Follow up on potential drug-induced liver injury (DILI) cases

Participants with transaminase increase combined with TBIL increase may be indicative of potential DILI and should be considered as clinically important events.

The threshold for potential DILI may depend on the participant's baseline aspartate aminotransferase (AST)/ALT and TBIL value; participants meeting any of the following criteria will require close follow-up as outlined below:

- For participants with normal alanine aminotransferase (ALT) and AST and TBIL value at baseline: AST or ALT $> 3.0 \times$ ULN combined with TBIL $> 2.0 \times$ ULN
- For participants with elevated AST or ALT or TBIL value at baseline: [AST or ALT $> 2 \times$ baseline] OR [AST or ALT $> 300 \text{ U/L}$] whichever occurs first combined with [TBIL $> 2 \times$ baseline AND $> 2.0 \times$ ULN]

As DILI is essentially a diagnosis of exclusion, other clinical causes of abnormal liver tests should be considered and their role clarified before DILI is assumed as the cause of liver injury.

A detailed history, including relevant information such as review of ethanol consumption, concomitant medications, herbal remedies, supplement consumption, history of any pre-existing liver conditions or risk factors, should be collected.

Laboratory tests should include ALT, AST, total bilirubin (TBIL) , direct and indirect bilirubin, glutamyltransferase (GGT), prothrombin time/ international normalized ratio (INR), alkaline phosphatase, albumin, and creatine kinase. If available, testing of Glutamate Dehydrogenase (GLDH) is additionally recommended.

Perform relevant examinations ((Ultrasound or MRI, Endoscopic Retrograde Cholangiopancreatography (ERCP)) as appropriate, to rule out an extrahepatic cause of cholestasis. Cholestasis is defined as an alkaline phosphatase (ALP) elevation $> 2.0 \times$ ULN with

R value < 2 in participants without bone metastasis, or elevation of the liver-specific ALP isoenzyme in participants with bone metastasis.

- Note: The R value is calculated by dividing the ALT by the ALP, using multiples of the ULN for both values. It denotes whether the relative pattern of ALT and/or ALP elevation is due to cholestatic ($R \leq 2$), hepatocellular ($R \geq 5$), or mixed ($R > 2$ and < 5) liver injury. For children, there are caveats to calculating the R-ratio as normal levels of ALP are higher than in adults with standard ranges varying by developmental age. In clinical situations where it is suspected that ALP elevations are from an extrahepatic source, the GGT can be used if available. GGT may be less specific than ALP as a marker of cholestatic injury, since GGT can also be elevated by enzyme induction or by ethanol consumption. It is more sensitive than ALP for detecting bile duct injury.

Table 6-2 Guidance on specific clinical and diagnostic assessments which can be performed to rule out possible alternative causes of observed LFT abnormalities.

Disease	Assessment
Hepatitis A, B, C, E	
 • IgM anti- hepatitis type A virus (HAV); Hepatitis B surface antigen (HBsAg), IgM & IgG anti - hepatitis B core (HBc),HBV deoxyriboNucleic acid (DNA); anti-hepatitis type C virus (HCV), HCV ribonucleic acid (RNA), IgM & Ig Ganti- hepatitis type E virus (HEV), HEV RNA
CMV, HSV, EBV infection	
 • IgM & IgG anti-CMV (Cytomegalovirus), IgM & IgG anti- herpes simplex virus (HSV); IgM & IgG anti- epstein-barr virus (EBV)
Autoimmune hepatitis	
 • antinuclear antibody (ANA) & anti-smooth muscle antibody (ASMA) titers, total Immunoglobulin M (IgM), Immunoglobulin G (IgG), Immunoglobulin E (IgE), Immunoglobulin A (IgA)
Alcoholic hepatitis	
 • Ethanol history, GGT, mean corpuscular volume (MCV), carbohydrate-deficient transferrin (CD-transferrin)
Nonalcoholic steatohepatitis	
 • Ultrasound or MRI
Hypoxic/ischemic hepatopathy	
 • Medical history: acute or chronic congestive heart failure (CHF), hypotension, hypoxia, hepatic venous occlusion. Ultrasound or MRI
Biliary tract disease	
 • Ultrasound or MRI, ERCP as appropriate
Wilson disease (if <40 yrs old)	
 • Ceruloplasmin
Hemochromatosis	
 • Ferritin, transferrin
Alpha-1-antitrypsin deficiency	
 • Alpha-1-antitrypsin

Other causes should also be considered based upon participants' medical history ((hyperthyroidism / thyrotoxic hepatitis – triiodothyronine (T3), tetraiodothyronine (T4), Thyroid Stimulating Hormone (TSH); Cardiovascular Disease (CVD) / ischemic hepatitis – ECG, prior hypotensive episodes; type 1 diabetes (T1D) / glycogenic hepatitis)).

Following appropriate causality assessments, as outlined above, the causality of the treatment is estimated as "probable" i.e. >50% likely, if it appears greater than all other possible causes of liver injury combined. The term "treatment-induced" indicates probably caused by the

treatment, not by something else, and only such a case can be considered a DILI case and should be reported as an SAE.

All cases confirmed on repeat testing meeting the laboratory criteria defined above, with no other alternative cause for LFT abnormalities identified, should be considered as “medically significant,” and thus, meet the definition of SAE and should be reported as SAE using the term “potential drug-induced liver injury.” All events should be followed up with the outcome clearly documented.

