10.1.2 Serious adverse events

An SAE is defined as any adverse event [appearance of (or worsening of any pre-existing)] undesirable sign(s), symptom(s), or medical conditions(s) which meets any one of the following criteria:

- fatal
- life-threatening

Life-threatening in the context of a SAE refers to a reaction in which the participant was at risk of death at the time of the reaction; it does not refer to a reaction that hypothetically might have caused death if it were more severe (please refer to the ICH-E2D Guidelines).

- results in persistent or significant disability/incapacity
- constitutes a congenital anomaly/birth defect
- requires inpatient hospitalization or prolongation of existing hospitalization, unless hospitalization is for:
 - routine treatment or monitoring of the studied indication, not associated with any deterioration in condition (e.g. hospitalization for relapse treatment)
 - elective or pre-planned treatment for a pre-existing condition that is unrelated to the indication under study and has not worsened since signing the informed consent
 - social reasons and respite care in the absence of any deterioration in the participant's general condition
 - treatment on an emergency outpatient basis for an event not fulfilling any of the definitions of a SAE given above and not resulting in hospital admission
- is medically significant, e.g. defined as an event that jeopardizes the participant or may require medical or surgical intervention to prevent one of the outcomes listed above

Medical and scientific judgment should be exercised in deciding whether other situations should be considered serious reactions, such as important medical events that might not be immediately life threatening or result in death or hospitalization but might jeopardize the participant or might require intervention to prevent one of the other outcomes listed above. Such events should be considered as "medically significant". Examples of such events are intensive treatment in an emergency room or at home for allergic bronchospasm, blood dyscrasias, or convulsions that do not result in hospitalization or development of dependency or abuse (please refer to the ICH-E2D Guidelines).

All malignant neoplasms will be assessed as serious under "medically significant" if other seriousness criteria are not met and the malignant neoplasm is not a disease progression of the study indication.

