10.1.3 SAE reporting

To ensure participant safety, every SAE, regardless of causality, occurring after the participant has provided informed consent and until 30 days after the last study visit must be reported to Novartis safety immediately, without undue delay, under no circumstances later than within 24 hours of learning of its occurrence. Detailed instructions regarding the submission process and requirements are to be found in the investigator folder provided to each site. Information about all SAEs is collected and recorded on the eSAE with paper backup Serious Adverse Event Report Form; all applicable sections of the form must be completed in order to provide a clinically thorough report.

All follow-up information for the SAE including information on complications, progression of the initial SAE and recurrent episodes must be reported as follow-up to the original episode

within 24 hours of the investigator receiving the follow-up information. An SAE occurring at a different time interval or otherwise considered completely unrelated to a previously reported one must be reported separately as a new event.

If the SAE is not previously documented in the Investigator's Brochure or Package Insert (new occurrence) and is thought to be related to the study treatment, a CMO & PS Department associate may urgently require further information from the investigator for health authority reporting. Novartis may need to issue an Investigator Notification (IN) to inform all investigators involved in any study with the same study treatment that this SAE has been reported.

Suspected Unexpected Serious Adverse Reactions (SUSARs) will be collected and reported to the competent authorities and relevant ethics committees in accordance with EU Guidance 2011/C 172/01 or as per national regulatory requirements in participating countries.

Any SAEs experienced after the 30 day period should only be reported to Novartis Safety if the investigator suspects a causal relationship to study treatment.

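### Section 6.5.2.1 puts causality inside the SAE decision for liver cases: its two rules conflict in one situation and, read literally, the first narrows Sections 10.1.2 and 10.1.3

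*Protocol*

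**What the plan says.** Protocol Section 6.5.2.1 sets laboratory criteria for potential drug-induced liver injury (DILI): ALT or AST above 3 x ULN with total bilirubin above 2 x ULN, or a baseline-adjusted version. It introduces them with "Participants with transaminase increase combined with TBIL increase may be indicative of potential DILI and should be considered as clinically important events". Two paragraphs after Table 6-2 then deal with SAE status.

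- **First paragraph.** After the causality work-up, treatment is a probable cause if it is ">50% likely, if it appears greater than all other possible causes of liver injury combined". Of a case that passes this test, "only such a case can be considered a DILI case and should be reported as an SAE".
- **Second paragraph.** "All cases confirmed on repeat testing meeting the laboratory criteria defined above, with no other alternative cause for LFT abnormalities identified" are to be considered medically significant and reported as SAEs under the term potential drug-induced liver injury.

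Section 10.1.2 lists the seriousness criteria. One is "requires inpatient hospitalization or prolongation of existing hospitalization" (with stated exceptions). Another covers an event that "is medically significant, e.g. defined as an event that jeopardizes the participant or may require medical or surgical intervention" to prevent one of the other listed outcomes. Section 10.1.3 requires reporting of "every SAE, regardless of causality, occurring after the participant has provided informed consent", within 24 hours of learning of it.

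In the SAP, Section 2.8.1 summarises serious TEAEs separately from drug-related TEAEs.

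**The concern.** Seriousness and causality are separate judgements, and the general safety sections of this protocol keep them apart. Section 6.5.2.1 does not. In its first paragraph a causality threshold decides whether a case is reported as an SAE. In its second, the condition "with no other alternative cause for LFT abnormalities identified" is attached to the medically significant category, which has no such condition in Section 10.1.2.

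Two consequences follow. A site cannot always obey both paragraphs. And two participants with the same confirmed laboratory picture, neither serious on another ground, can differ in SAE status on attribution alone. SAEs are a secondary endpoint, liver transaminase elevation is a named risk, and the trial is open-label with no control arm against which under-classification might show. Section 6.5.2.1 also does not say when the 24-hour clock starts for a case whose SAE status awaits the work-up.

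**Working it through.** The plan states no figure on this point, so the main check sets the rules side by side.

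**Step 1. Two paragraphs, four situations.** Take a case that meets the laboratory criteria, is confirmed on repeat and is not serious for any other reason. The second paragraph gives a sufficient condition: it says which cases are SAEs, not that no others are. Where an alternative cause is identified, it is silent.

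| Drug causality | Alternative cause identified? | First paragraph | Second paragraph | Result |
|---|---|---|---|---|
| Above 50% | No | SAE | SAE | Agree |
| Above 50% | Yes | SAE | Silent | SAE, no conflict |
| 50% or less | No | Not an SAE | SAE | **Conflict** |
| 50% or less | Yes | Not an SAE | Silent | Not an SAE within 6.5.2.1 |

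The paragraphs conflict in one situation of four, the third row. It can arise when other causes are suspected but none is established. Table 6-2 lists assessments that can be performed, so an incomplete work-up could leave a case there.

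**Step 2. Against Sections 10.1.2 and 10.1.3.** No criterion in the bulleted list of Section 10.1.2 depends on whether the drug caused the event. (That section separately treats suspected transmission of an infectious agent via a medicinal product as serious; this does not bear on liver cases.) Section 10.1.3 governs events already classed as serious. The friction with it is therefore indirect: the word *only* can stop a case from being classed as serious, after which the rule on reporting regardless of causality never applies.

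**Step 3. What depends on the flag.** The SAE flag feeds the serious-TEAE summary in SAP 2.8.1, which is exempt from the 45-day safety cutoff, and the 24-hour report. These outputs do not depend on it:
- AE recording under Section 10.1.1;
- follow-up of liver triggers under Section 10.2.1, which applies whatever the AE or SAE classification;
- the special-interest tables in SAP 2.8.1.1, which use search terms;
- the ALT, AST and bilirubin tabulations in SAP Tables 2-8 and 2-9.

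Table 2-9 shows the analytes in separate rows, with no combined category.

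**Step 4. Scale.** Inputs: about 100 participants (Section 3) and 8.0% with transaminases at or above 3 x ULN on 0.5 mg (Section 1.1), so 100 x 0.08 = 8 participants. The documents give no rate for transaminases and bilirubin together. Assume a joint rate p of 0.1% to 1%. The expected count is 100p, and P(at least one) = 1 - (1 - p)^100.

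| Assumed p | Expected cases | P(at least one) |
|---|---|---|
| 0.1% | 0.1 | 9.5% |
| 0.25% | 0.25 | 22.1% |
| 0.5% | 0.5 | 39.4% |
| 1% | 1.0 | 63.4% |

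P(zero or one) = (1 - p)^100 + 100p(1 - p)^99, which is 99.5% at p = 0.1% and 73.6% at p = 1%. These are all combined cases. Those affected by the wording are a subset: drug causality judged at 50% or less, and no other seriousness criterion met.

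**The case against.** The strongest reply is that this is loose drafting with little consequence. Section 6.5.2.1 nowhere disapplies Section 10.1.2. A liver case with another cause is still an SAE if it is fatal, life-threatening, disabling, hospitalised within the terms of that section, or judged medically significant. The second paragraph's term is *potential* DILI, so the paragraphs might be meant as two tiers, confirmed and potential. The conflicting situation should be uncommon, because a case with no identified alternative will often be judged probably drug-related. Exclusion of active hepatitis and Child-Pugh class C disease removes some competing causes.

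Most of this stands and limits the size of the point. The two-tier reading does not remove the problem: if *only* the probable cases are to be reported as SAEs, the second tier cannot be reported as well.

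A reader might also infer more than the documents support:

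- **That the paragraphs contradict each other whenever an alternative cause is present**, for example drug 70% and hepatitis 30%. They do not. The first paragraph makes that case an SAE and the second is silent.
- **That liver injury with another cause drops out of the data, or that the serious-TEAE table becomes a drug-related table.** The outputs listed in Step 3 still capture the injury, and otherwise-serious cases keep their flag.
- **That 24-hour reporting is suspended until the work-up ends.** No sentence says so. The order of the text invites that practice, but the delay is an inference.

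**Conclusion.** The point holds as an inconsistency in the reporting rules. The first paragraph makes SAE status depend on a causality threshold. It conflicts with the second for a repeat-confirmed case with no alternative identified and drug causality at 50% or less. Read literally, it also narrows Sections 10.1.2 and 10.1.3.

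The numerical effect is small: mainly cases not otherwise serious, probably zero or one of about 100 participants. That rests on the assumed joint rate of 0.1% to 1% and on Section 10.1.2 continuing to catch the other cases. Purely as an illustration with an assumed count, one missed case would move the serious hepatic rate from 1/100 (Clopper-Pearson 95% interval 0.03% to 5.4%) to 0/100 (upper limit 3.6%). The primary endpoint is unaffected. The reason to act is that sites are given rules they cannot always follow together, on a secondary safety endpoint with a 24-hour reporting duty.

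**What to change.** Reconcile the passages in Section 6.5.2.1.

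1. In the first paragraph, keep the definition of a DILI case and delete the closing words on SAE reporting, so that the 50% test governs only the DILI diagnosis term.
2. Replace the second paragraph with one rule, for example: *Seriousness follows Section 10.1.2 whatever the attribution. A case that meets the laboratory criteria of this section on repeat testing is treated as medically significant and is reported within 24 hours of that confirmation, without waiting for the Table 6-2 work-up. Causality is recorded separately and updated later. The event term is potential drug-induced liver injury while no other cause is established, and the established diagnosis otherwise.*
3. Add that a case already serious on another criterion keeps the clock in Section 10.1.3.

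Limiting the term in this way respects the protocol's statements that DILI is a diagnosis of exclusion (Section 6.5.2.1) and that events should be described by diagnosis where possible (Section 10.1.1).

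The cost is protocol wording and possibly one or two extra SAE reports with an alternative cause. Only classification and reporting change. Optionally, a combined ALT/AST-plus-bilirubin row in SAP Table 2-9 would give a count free of attribution; it is not needed to resolve the conflict.
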